#### **6.4.7 T cell and NK cell counts**

The summary of the mean (+/-SD) for the T cell (CD3, CD4, CD8) and NK cell counts (CD16 and CD56) will be shown over time in a figure where T-cell and NK-cell data are available.

#### **6.4.8 PD-L1 (CD274), PD-1, B7-1( CD80)**

The appropriate outputs, summary or listing, will be produced for studies with atezolizumab.

#### **6.4.9 Pharmacokinetic Samples, HAHA, HACA and ATA**

PK serum concentration of obinutuzumab, atezolizumab, lenalidomide, polatuzumab vedotin, venetoclax, Idasanutlin will be analysed. Immunogenicity to obinutuzumab, atezolizumab, Rituximab and polatuzumab vedotin will be explored analytically based on the immune response relative to the HAHA, HACA or ATA prevalence at baseline.

#### **6.4.10 Immunoglobulins**

##### **6.4.10.1 Immunoglobulin Depletion and Recovery**

Immunoglobulin depletion and recovery during follow up will be derived according to the following:

**Lower immunoglobulin thresholds:**

- IgA: 0.5 g/L
- IgM: 0.3 g/L
- IgG: 5 g/L

- **Depletion after Baseline:**
  - YES = (Lab value < Lower Threshold)
  - NO = (Lab value >= Lower Threshold)
  
- **Recovery:**
  - YES = (Lab value >= Lower Threshold), and the lab value was collected after the last dose of antibody and patient was previously depleted
  - NO = (Lab value < Lower Threshold) and the lab value was collected after the last dose of antibody and patient was previously depleted (only displayed for last value in patient listing)

Recovery (single) is the first recovery based on definition above which is not followed exclusively by further depletion i.e. recovery at a visit cannot be immediately followed by depletion, or a missing assessment, but only by recovery at the next visit. Time to single recovery is defined as the number of days between the date of last dose of antibody and date of single recovery. In case a patient was not depleted at the last dose of antibody no time to single recovery will be calculated. Where no immunoglobulin value occurs at the last dose of antibody, the next valid immunoglobulin assessment will be taken. If there are multiple immunoglobulin records at a visit, the last immunoglobulin assessment will be retained provided there is a valid identifier. If a study does not have a valid identifier, the lowest immunoglobulin value at the visit will be used instead. Recovery will be assessed up to the first day of NALT.

Analysis will be done separately for IgA, IgM and IgG. No time windows will be applied. Only visits with a valid date and non-missing values will be considered for the derivation of immunoglobulin recovery and depletion. Immunoglobulins with no associated time that are collected on the same day as the last dose of the antibody will be assumed to be pre-dose.

Descriptive statistics (n, mean, sd, median, range) will be produced at each timepoint where immunoglobulin values are available to describe the course of IgA, IgG and IgM.

An output will be produced to look at the proportion of patients with low immunoglobulin levels at each timepoint where immunoglobulin values are available.

## 7 Pharmacokinetic Analyses

PK analyses will be defined in a separate analysis plan.

## **8 Protocol Deviations**

Major protocol deviations will be taken from the PDMS system. All major deviations from PDMS will be listed and summarized and will be reported in the CSR.

## **9 References**

## **10 Output Template**

This section will contain all output templates, including those produced by STREAM.

### 10.1 Output 1 Enrollment by Country and Investigator

Country, Investigator Number / Name	Treatment Group 1 (N=nn)	Treatment Group 2 (N=nn)
Country 1	nn (xx.x%)	nn (xx.x%)
xxxxx / LastName, FirstName	nn (xx.x%)	nn (xx.x%)
xxxxx / LastName, FirstName	nn (xx.x%)	nn (xx.x%)
...		
Country 2	nn (xx.x%)	nn (xx.x%)
xxxxx / LastName, FirstName	nn (xx.x%)	nn (xx.x%)
...		

Programming notes:

1. Analysis population: ITT
2. Template ID: ENT02
3. Program name: T\_EN

## 10.2 Output 2 Patient Disposition

Status	Treatment Group 1 (N=nn)	Treatment Group 2 (N=nn)
Alive on Induction Phase	nn (xx.x%)	nn (xx.x%)
Alive on Maintenance/Consolidation Phase	nn (xx.x%)	nn (xx.x%)
Alive in follow-up	nn (xx.x%)	nn (xx.x%)
Discontinued study	nn (xx.x%)	nn (xx.x%)
Reason 1	nn (xx.x%)	nn (xx.x%)
Reason 2	nn (xx.x%)	nn (xx.x%)
Reason 3	nn (xx.x%)	nn (xx.x%)
Reason 4	nn (xx.x%)	nn (xx.x%)
...	nn (xx.x%)	nn (xx.x%)

### Programming notes:

1. Analysis population: ITT
2. Template ID: DST01
3. Program name: T\_DS
4. CRF: Study Drug Administration, Maintenance Phase Completion, Consolidation Phase Completion, Study Drug Discontinuation
5. Alive on induction phase: subject took at least one dose of study medicine and was on induction phase (at least one study treatment Induction Phase Completion or discontinuation was **not** recorded AND study treatment discontinuation was **not** recorded on eCRF)
6. Alive on maintenance/consolidation phase: subject took at least one dose of study medicine on maintenance/consolidation phase and was on maintenance/consolidation phase (at least one maintenance study treatment discontinuation was **not** recorded and study discontinuation was **not** recorded on eCRF)
7. Alive in follow-up: all study treatment discontinuation was recorded but study discontinuation was **not** recorded on eCRF
8. Discontinued study: study discontinuation was recorded on eCRF
9. For BH29812, no maintenance/consolidation for DLBCL patients

### 10.3 Output 3 Analysis Populations

	Treatment Group 1 (N=nn)	Treatment Group 2 (N=nn)
ITT (Enrolled Population)		
Safety Evaluable Population		
Total Exclusions		
Reason 1		
Reason 2		
Efficacy Evaluable Population		
Total Exclusions		
Reason 1		
Reason 2		

### 10.4 Output 4 Listing of Patients Excluded from Analysis Populations

Center/ Patient ID	Age/Sex/Race	Population Excluded From	Reason

## 10.5 Output 5 Study Drug Completion Status and Reasons of Withdrawals from Study Drug

Status	Treatment Group 1 (N=nn)	Treatment Group 2 (N=nn)
Induction Phase		
Discontinued study drug 1	nn (xx.x%)	nn (xx.x%)
Reason 1	nn (xx.x%)	nn (xx.x%)
Reason 2	nn (xx.x%)	nn (xx.x%)
Reason 3	nn (xx.x%)	nn (xx.x%)
Reason 4	nn (xx.x%)	nn (xx.x%)
...	nn (xx.x%)	nn (xx.x%)
Discontinued study drug 2	nn (xx.x%)	nn (xx.x%)
Reason 1	nn (xx.x%)	nn (xx.x%)
Reason 2	nn (xx.x%)	nn (xx.x%)
...	nn (xx.x%)	nn (xx.x%)
...		
Maintenance/Consolidation Phase		
Discontinued study drug 1	nn (xx.x%)	nn (xx.x%)
Reason 1	nn (xx.x%)	nn (xx.x%)
Reason 2	nn (xx.x%)	nn (xx.x%)
...	nn (xx.x%)	nn (xx.x%)

Programming notes:

1. Analysis population: Safety
2. Template ID: DST01
3. Program name: T\_DS\_DRG
1. CRF: Study Drug Administration

## 10.6 Output 6 Duration on Treatment and Follow-up

	Treatment Group 1 (N=nn)	Treatment Group 2 (N=nn)
Duration on Treatment (months)		
n	nnn	nnn
Mean (SD)	xx.x (xx.x)	xx.x (xx.x)
Median	xx.x	xx.x
Min-max	xx-xx	xx-xx
Duration of Study Period (months)		
n	nnn	nnn
Mean (SD)	xx.x (xx.x)	xx.x (xx.x)
Median	xx.x	xx.x
Min-max	xx-xx	xx-xx

Duration on Treatment was calculated as time from the first dose date until the last dose date + 1 day. Patients without any study medication were excluded.

Duration of Study Period was calculated as time from the first dose date to the last dates the patients were known to be alive or their death dates if died + 1 day.

Programing notes:

1. Analysis population: Safety
2. Template ID: DMT01
3. Program name: T\_DS\_DUR
4. Use descriptive method
5. CRF: Study Drug Administration
6. Duration of study period: Patients for whom no death is captured on the clinical database use the date they were known to be alive (see Section 2.3.7).

## Output 7 Listing of Patients Who Discontinued Early from Study Drug

Center/ Patient ID	Age/Sex/Race	Drug*	Date of First Study Drug Administration	Day of Last Study Drug Administration	Day of Study Discontinuation*	Reason for Discontinuation from study drug*	Reason for Discontinuation from study
		Treatment1		12	14	Adverse event	Adverse event
		Treatment2		36	65	Lost to follow-up	Lost to follow-up
		Treatment3		36	65	Lost to follow-up	Lost to follow-up

### Programing notes:

1. Analysis population: Safety
2. Template ID: DSL02
3. Program name: L\_DS\_DRG
4. Reason for Discontinuation from study: leave blank if a patient discontinued from study drug but not discontinued from study
5. Date of first study drug administration: use the first date of any drug
6. Day of last study drug administration: use the day for the certain drug
7. \*: one line for each drug

## 10.8 Output 8 Major Protocol Deviations

	Treatment Group 1 (N=nn)	Treatment Group 2 (N=nn)			
Total number of patients with at least one major Protocol Deviation	nn (xx.x%)	nn (xx.x%)			
Total number of major protocol deviations	nn	nn			
Inclusion Criteria					
Age criteria	nn (xx.x%)	nn (xx.x%)	nn (xx.x%)	nn (xx.x%)	nn (xx.x%)
Exclusion Criteria					
Pregnancy criteria	nn (xx.x%)	nn (xx.x%)	nn (xx.x%)	nn (xx.x%)	nn (xx.x%)
Sodium > 180mg	nn (xx.x%)	nn (xx.x%)	nn (xx.x%)	nn (xx.x%)	nn (xx.x%)
Procedural					
Incorrect dose	nn (xx.x%)	nn (xx.x%)	nn (xx.x%)	nn (xx.x%)	nn (xx.x%)

Programing notes:

1. Analysis population: ITT
2. Template ID: PDT01
3. Program name: T\_DV

## 10.9 Output 9 Listing of Major Protocol Deviations

Center/ Patient ID	Age/Sex/Race	Category	Subcategory
[REDACTED]			
...			

Programing notes:

1. Analysis population: ITT
2. Program name: L\_DV

## 10.10 Output 10 Demographics and Baseline Characteristics

	Treatment Group 1 (N=nn)	Treatment Group 2 (N=nn)
Age (yr)		
n	nnn	nnn
Mean (SD)	xx.x (xx.x)	xx.x (xx.x)
Median	xx.x	xx.x
Min-max	xx-xx	xx-xx
Age group (yr)		
n	nnn	nnn
18-40	nn (xx.x%)	nn (xx.x%)
41-64	nn (xx.x%)	nn (xx.x%)
≥65	nn (xx.x%)	nn (xx.x%)
Sex		
n	nnn	nnn
Male	nn (xx.x%)	nn (xx.x%)
Female	nn (xx.x%)	nn (xx.x%)
Weight (kg) at baseline		
n	nnn	nnn
Mean (SD)	xx.x (xx.x)	xx.x (xx.x)
Median	xx.x	xx.x
Min-max	xx-xx	xx-xx
Height (cm) at baseline		
n	nnn	nnn
Mean (SD)	xx.x (xx.x)	xx.x (xx.x)
Median	xx.x	xx.x
Min-max	xx-xx	xx-xx
ECOG Category at baseline		
n	nnn	nnn
0	nn (xx.x%)	nn (xx.x%)
≥1	nn (xx.x%)	nn (xx.x%)
...		
...		

Programming notes:

1. Analysis population: ITT
2. Template ID: DMT01
3. Program name: T\_DM
4. CRF: Demographics, ECOG Performance Status, Vital Signs
5. See section 4.1 for identifying further variables that may be included in this output.

## **10.11 Output 11 Baseline Disease Characteristics and Prognostic Markers**

	Treatment Group 1 (N=nn)	Treatment Group 2 (N=nn)
Duration since initial diagnosis* (months)		
n	nn	nn
Mean (SD)	xx.x (xx.x)	xx.x (xx.x)
Median	xx.x	xx.x
Min-max	xx-xx	xx-xx
Ann Arbor Stage at initial diagnosis		
n	nn	nn
Stage 1	nn (xx.x%)	nn (xx.x%)
Stage 2	nn (xx.x%)	nn (xx.x%)
Stage 3	nn (xx.x%)	nn (xx.x%)
Stage 4	nn (xx.x%)	nn (xx.x%)
Initial FL grade**		
n	nn	nn
Grade 1	nn (xx.x%)	nn (xx.x%)
Grade 2	nn (xx.x%)	nn (xx.x%)
Grade 3a	nn (xx.x%)	nn (xx.x%)
Ungraded	nn (xx.x%)	nn (xx.x%)
Duration since diagnosis at study entry* (months)		
n	nn	nn
Mean (SD)	xx.x (xx.x)	xx.x (xx.x)
Median	xx.x	xx.x
Min-max	xx-xx	xx-xx
Ann Arbor Stage at study entry		
n	nn	nn
Stage 1	nn (xx.x%)	nn (xx.x%)
Stage 2	nn (xx.x%)	nn (xx.x%)
Stage 3	nn (xx.x%)	nn (xx.x%)
Stage 4	nn (xx.x%)	nn (xx.x%)
FL Grade at study entry**		
n	nn	nn
Grade 1	nn (xx.x%)	nn (xx.x%)
Grade 2	nn (xx.x%)	nn (xx.x%)
Grade 3a	nn (xx.x%)	nn (xx.x%)
Ungraded	nn (xx.x%)	nn (xx.x%)
Prior anti-lymphoma therapy		
N	nn	nn

	Treatment Group 1 (N=nn)	Treatment Group 2 (N=nn)
Yes	nn (xx.x%)	nn (xx.x%)
No	nn (xx.x%)	nn (xx.x%)
Lines of prior anti-lymphoma therapy		
N	nn	nn
1	nn (xx.x%)	nn (xx.x%)
2	nn (xx.x%)	nn (xx.x%)
>=3	nn (xx.x%)	nn (xx.x%)
Prior anti-CD20 agents		
N	nn	nn
Yes	nn (xx.x%)	nn (xx.x%)
No	nn (xx.x%)	nn (xx.x%)
Prior autologous stem cell transplant		
N	nn	nn
Yes	nn (xx.x%)	nn (xx.x%)
No	nn (xx.x%)	nn (xx.x%)
Prior cancer radiotherapy		
N	nn	nn
Yes	nn (xx.x%)	nn (xx.x%)
No	nn (xx.x%)	nn (xx.x%)
Total number of risk factors for IPI at initial Diagnosis (DLBCL)***		
N	nn	nn
Low (0 to 2)	nn (xx.x%)	nn (xx.x%)
High (3 to 5)	nn (xx.x%)	nn (xx.x%)
Total number of risk factors for IPI at study entry (DLBCL)***		
N	nn	nn
Low (0 to 2)	nn (xx.x%)	nn (xx.x%)
High (3 to 5)	nn (xx.x%)	nn (xx.x%)
Total number of risk factors for FLIPI at initial Diagnosis (FL)**		
N	nn	nn
Low (0 or 1)	nn (xx.x%)	nn (xx.x%)
Intermediate (2)	nn (xx.x%)	nn (xx.x%)
High (3 to 5)	nn (xx.x%)	nn (xx.x%)
Total number of risk factors for FLIPI at study entry (FL)***		

	Treatment Group 1 (N=nn)	Treatment Group 2 (N=nn)
N	nn	nn
Low (0 or 1)	nn (xx.x%)	nn (xx.x%)
Intermediate (2)	nn (xx.x%)	nn (xx.x%)
High (3 to 5)	nn (xx.x%)	nn (xx.x%)
Total number of risk factors for FLIPI2 at initial Diagnosis (FL)**		
N	nn	nn
Low (0 or 1)	nn (xx.x%)	nn (xx.x%)
Intermediate (2)	nn (xx.x%)	nn (xx.x%)
High (3 to 5)	nn (xx.x%)	nn (xx.x%)
Total number of risk factors for FLIPI2 at study entry (FL)***		
N	nn	nn
Low (0 or 1)	nn (xx.x%)	nn (xx.x%)
Intermediate (2)	nn (xx.x%)	nn (xx.x%)
High (3 to 5)	nn (xx.x%)	nn (xx.x%)
B-Symptom: unexplained fever greater than 38 degree C		
N	nn	nn
Yes	nn (xx.x%)	nn (xx.x%)
No	nn (xx.x%)	nn (xx.x%)
B-Symptom: night sweats		
N	nn	nn
Yes	nn (xx.x%)	nn (xx.x%)
No	nn (xx.x%)	nn (xx.x%)
B-Symptom: unexplained weight loss greater than 10% in less than or equal 6 months		

	Treatment Group 1 (N=nn)	Treatment Group 2 (N=nn)
N	nn	nn
Yes	nn (xx.x%)	nn (xx.x%)
No	nn (xx.x%)	nn (xx.x%)
SPD		
n	nnn	nnn
Mean (SD)	xx.x (xx.x)	xx.x (xx.x)
Median	xx.x	xx.x
Min-max	xx-xx	xx-xx
Bulk Disease		
n	nnn	nnn
Yes	nn (xx.x%)	nn (xx.x%)
No	nn (xx.x%)	nn (xx.x%)
LDH		
n	nnn	nnn
Mean (SD)	xx.x (xx.x)	xx.x (xx.x)
Median	xx.x	xx.x
Min-max	xx-xx	xx-xx
Bone marrow involvement		
n	nnn	nnn
Yes	nn (xx.x%)	nn (xx.x%)
No	nn (xx.x%)	nn (xx.x%)

Programming notes:

1. Analysis population: ITT
2. Template ID: DMT01
3. Program name: T\_DM\_HIS
4. \*Duration since initial diagnosis : time from date of initial histological diagnosis to date of first study drug
5. \*Duration since diagnosis at study entry : time from date of diagnosis at study entry to date of first study drug
6. Generate this output for DLBCL and FL respectively (\*\*: only applicable for FL groups, \*\*\*: only applicable for DLBCL groups)
7. Lines of prior anti-lymphoma chemotherapy: maximum lines of anti-lymphoma therapy
8. CRF: NHL history, NHL prognostic factors, prior anti-lymphoma therapy, prior anti-CD20 agents, prior autologous stem cell transplant, prior anti-lymphoma radiotherapy
9. Further variables that may be included here are listed in section 4.2

Note: For FLIPI/IP category, follow study SMT instruction if different from the mockup.

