#### **4.5.2 Medical History and Demographic Data**

Medical history includes clinically significant diseases, surgeries, reproductive status, smoking history, and alcohol and drug abuse. In addition, all medications (e.g., prescription drugs, over-the-counter drugs, herbal or homeopathic remedies, nutritional supplements) used by the patient within 14 days prior to the screening period will be recorded.

Demographic data will include age, sex, and self-reported race/ethnicity.

The following clinical parameters relative to disease history, diagnosis, and prognostic indices will be recorded at screening:

- Date of initial diagnosis
- ECOG performance status (see [Appendix 7](#))
- Ann Arbor staging (see [Appendix 8](#))
- For patients with FL: FLIPI and FLIPI2 (see [Appendix 9](#))
- For patients with DLBCL: IPI (see [Appendix 9](#))
- B symptoms (unexplained fever >38°C, night sweats, and unexplained weight loss > 10% of body weight over 6 months)
- Previous lines of anti-lymphoma treatment as well as response to prior therapy, date of disease progression in relation to start date of prior treatment, and date of last dose of prior treatment

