## Appendix 9 Follicular Lymphoma International Prognostic Index and International Prognostic Index (cont.)

**Table 2 Follicular Lymphoma International Prognostic Index 2**

FLIPI2 Risk Factor	
Bone marrow involvement	
Age > 60 years	
$\beta_2$ microglobulin > 1 × ULN	
Anemia (hemoglobin < 120 g/L)	
Longest diameter of largest involved node > 6 cm	
FLIPI2 Risk Group	Number of FLIPI2 Risk Factors
Low	0
Intermediate	1 or 2
High	3 to 5

FDG = fluorodeoxyglucose; FLIPI2 = Follicular Lymphoma International Prognostic Index 2; PET = positron emission tomography; ULN = upper limit of normal.

Note: The results of FDG-PET should not be taken into account for calculation of FLIPI2 since this prognostic score was established without FDG-PET.

Adapted from:

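### SAP Output 11 groups FLIPI2 by the FLIPI cut-offs, not those in protocol Appendix 9, and marks the FL study-entry rows as DLBCL-only

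*SAP*

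**What the plan says.** Protocol section 4.5.2 lists the prognostic indices to be recorded at screening, including "For patients with FL: FLIPI and FLIPI2". Appendix 9 defines the risk groups of each index. Table 1 (FLIPI) has low for 0 or 1 factor, intermediate for 2 and high for 3 to 5. Table 2 (FLIPI2), under its column "Number of FLIPI2 Risk Factors", has low for 0, "Intermediate 1 or 2", and high for 3 to 5.

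SAP Output 11 (section 10.11) is the baseline disease characteristics table. It has two FLIPI2 blocks, "Total number of risk factors for FLIPI2 at initial Diagnosis (FL" and "Total number of risk factors for FLIPI2 at study entry (FL". In both, low is 0 or 1, the middle row reads "Intermediate (2" with no other score in it, and high is 3 to 5.

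Programming note 6 of the same output has the table produced once for DLBCL and once for FL. Two asterisks mean a row is for FL groups; three mean it is "only applicable for DLBCL groups". The FLIPI and FLIPI2 initial-diagnosis rows carry two asterisks. The FLIPI and FLIPI2 study-entry rows, although labelled FL, carry three.

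A closing note adds: "For FLIPI/IP category, follow study SMT instruction if different from the mockup".

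**The concern.** FLIPI and FLIPI2 are separate indices with different low and intermediate groups, and the SAP applies one set of cut-offs to both. An FL patient with a single FLIPI2 factor is intermediate risk under the protocol and low risk in the SAP table. The shift runs one way only, so the FL cohort can look lower-risk than the protocol's definition makes it, never higher-risk.

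Because the cohort has no concurrent control, the baseline table is where a reader judges what kind of FL patients were treated. A reader who assumes that the printed groups follow Appendix 9 would be misled. A reader who notices the printed range still could not recover the protocol grouping, because scores 0 and 1 share one row.

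The mark on the study-entry rows is a second defect in the same block. For relapsed or refractory patients, study entry is the time point that describes the cohort as treated, and it is the one at which the protocol records both indices. Read literally, note 6 removes those rows from the FL version of the table.

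**Working it through.** There is no sample size, power or interval to reproduce. The check is to run every possible FLIPI2 score (0 to 5, from five risk factors) through both definitions.

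Inputs: protocol Appendix 9 Table 2 for the protocol FLIPI2 groups; SAP Output 11, both FLIPI2 blocks, for the SAP groups; protocol Appendix 9 Table 1 for the FLIPI groups.

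| Score | Protocol FLIPI2 | SAP FLIPI2 | Protocol FLIPI | SAP agrees with protocol FLIPI2? |
|---|---|---|---|---|
| 0 | Low | Low | Low | yes |
| 1 | Intermediate | Low | Low | no |
| 2 | Intermediate | Intermediate | Intermediate | yes |
| 3 | High | High | High | yes |
| 4 | High | High | High | yes |
| 5 | High | High | High | yes |

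One score of six changes group. The SAP column matches the protocol's FLIPI column at every score, so the SAP is using the FLIPI grouping. How that came about the documents do not say.

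Next, the marks:

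| Row in Output 11 | Label | Mark | Meaning under note 6 |
|---|---|---|---|
| FLIPI, initial diagnosis | FL | two asterisks | FL only |
| FLIPI, study entry | FL | three asterisks | DLBCL only |
| FLIPI2, initial diagnosis | FL | two asterisks | FL only |
| FLIPI2, study entry | FL | three asterisks | DLBCL only |

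Both study-entry rows contradict their own label. For the FLIPI2 study-entry row the two defects are alternatives. A programmer who follows the mark omits the row, and nobody is misgrouped there. One who follows the label prints it with score 1 under low. Neither route gives the protocol's result.

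Size: the documents contain no FLIPI2 distribution, so the number of patients with exactly one factor cannot be worked out. Among the 40 FL patients planned for expansion it could in principle be any number from 0 to 40.

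Reach: FLIPI2 does not enter the primary analysis (protocol 6.5.1, SAP 5.1) or the interim analysis (protocol 6.8, SAP 5.4). SAP 3.5 allows for FLIPI and IPI subgroups and does not name FLIPI2.

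**The case against.** The strongest point against is the closing note under Output 11, which lets an SMT instruction replace the mock-up categories. That instruction is not in the documents and may already use the right cut-offs. This stands as a limit on certainty: a reader might infer that one-factor patients will definitely be reported as low risk, and the documents support that only on condition that the mock-up is followed. It does not cure the defect, because the note gives no cut-offs and does not point to Appendix 9. The update log does not help either: it sets the labels for FLIPI and IPI but records no FLIPI2 regrouping.

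Second, the mock-up does not aim to reproduce Appendix 9 throughout, since it also reduces IPI from four groups to two. That reduction, however, merges adjacent protocol groups (0 to 2, 3 to 5) and moves no boundary. The FLIPI2 rows keep three groups with the protocol's names and move one boundary.

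Third, the table prints the score range beside each label, and the analysis can be rerun from the recorded risk factors. Both are true. They make the error visible and recoverable, which bears on its weight and not on its existence.

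Fourth, the protocol records FLIPI2 at screening, so the initial-diagnosis block may be sparsely filled, and the FL label makes omission of the study-entry rows the less natural reading. Both are fair, but the grouping still needs correcting in whichever block is printed.

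A reader might also infer that the misgrouping biases the comparison of the FL complete response rate with the 40% level or with historical controls, or distorts index-based subgroups. The documents do not support this: FLIPI2 adjusts or stratifies none of those analyses.

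**Conclusion.** Wrong as written, minor. The FLIPI2 cut-offs in SAP Output 11 conflict with protocol Appendix 9 Table 2 at score 1, and two rows labelled FL carry a DLBCL-only mark. If the mock-up is followed, the FL baseline table either shows one-factor patients as low instead of intermediate risk or omits the study-entry indices.

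The damage is limited to the descriptive risk profile of the FL cohort. No estimate, confidence interval, sample size or stopping decision depends on it.

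The conclusion rests on two assumptions. One is that no SMT instruction has overridden the categories. The other is that the harmonised SAP governs this study: its introduction does not list BH39147, but its tables of selected adverse events and adverse events of special interest (section 6.2.2) have a column for it.

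**What to change.** In SAP Output 11, set both FLIPI2 blocks (initial diagnosis and study entry) to Low (0), Intermediate (1 or 2), High (3 to 5), citing protocol Appendix 9 Table 2. Change the mark on the FLIPI and FLIPI2 study-entry rows from three asterisks to two. If an SMT instruction on these categories exists, check it against Appendix 9 at the same time.

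The cost is four small template edits and the matching change in the baseline table program. No data collection changes and no other analysis needs to be rerun.
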